Castrate-resistant PCA presents a spectrum of disease ranging from rising prostate-specific antigen (PSA) levels in the absence of metastases or symptoms and despite androgen-deprivation therapy, to metastases and significant debilitation from cancer symptoms. Castrate-resistant PCA is usually suspected in patients with new symptoms on androgen deprivation therapy, with a rising PSA, or with new evidence of disease on bone scans or CT scans.

Novel hormonal agents such as abiraterone acetate and enzalutamide improved survival significantly for patients with metastatic castration-resistant prostate cancer. Nevertheless, median survival is limited to 35 months after initiation of therapy. Therefore, it is beneficial to have a more accurate diagnostic measure to assess time to progression, either for patients to receive optimal therapy regimes or for studies to have a more accurate time to progression measure (5, 6). For this reason, the PCWG3 defined criteria for progression of the disease. The most challenging task is the assessment of bone metastases in the early phase of therapy due to common onset of a flare phenomenon. The flare phenomenon refers to the increase in radiotracer uptake at previously diagnosed or new previously undetected lesions soon after initiating therapy. Increased uptake is transient, but variable, lasting between three and six months. It is thought that the increase is a response to bone deposition and repair at treated sites. This increase in signal makes the distinction between progression of bone lesions or increased metastatic spread and successful treatment considerably difficult. In CT scans these lesions would appear osteosclerotic and thus could not be distinguished between therapy response and progression. For this reason, the PCWG3 defined progression as “appearance of at least two new lesions on first post-treatment scan, with at least two additional lesions on the next scan (2+2 rule). If at least two additional new lesions are seen on the next (confirmatory) scan, the date of progression is the date of the first post-treatment scan, when the first two new lesions were documented.” This implicates that progression needs to be dated back and diagnosis of progression is delayed by three months typically.

This highlights the critical need to precisely and accurately determine between flare and progressive disease after onset of therapy.

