3. Serum creatinine < 2.0
4. BMI < 35kg/m²
5. Sign informed consent

Exclusion Criteria:

History of anaphylactoid reaction to iodinated contrast material

All MDCT examinations will be performed using a third-generation dual-source dual-energy MDCT platform (Somatom Definition FORCE, Siemens Healthcare, Forchheim, Germany). Each patient will receive an unenhanced dual energy scan followed by a contrast-enhanced dual energy scan as part of clinical routine work up (Table 1). The preliminary unenhanced dual energy scan, which is currently *not* part of our routine clinical protocol, will provide necessary information for the baseline material density quantitative analysis of the bone marrow. For the contrast-enhanced scan, each patient will be scanned in a caudocranial direction during the hepatic venous phase 60-70 seconds after the start of contrast medium injection. No change in the contrast material injection protocol will be performed for this study.

Patients will be examined with a dual-energy protocol at baseline (i.e., before starting therapy), and during the first and second follow up scans in order to differentiate between patients with partial remission, stable, or progressive disease.

Table 1. Details of the dual-energy CT scan protocols.

		kVp	Pitch	Effective mAs	mAs / rotation	Relative CTDI _{vol} (%)	Relative DLP (%) [*]
1st scan	Tubes 1 + 2	120	1	200	200	100	100
	Tube 1	100	1				
	Tube 2	150	1				
2nd scan	Tubes 1 + 2	120	1	200	200	100	100
	Tube 1	100	1				
	Tube 2	150	1				

Images will be reconstructed following conventional protocols and will include 5.0 and 0.6 mm slice thickness using filtered back projection (FBP) and commercially available iterative reconstruction (advanced modeled iterative reconstruction algorithm [ADMIRE]).

In addition, we will collect relevant clinical and demographic patient's information, such as prostate cancer related parameters, medical record number, age, gender, and body weight, height and body mass index. We will also collect information regarding the CT parameters, radiation dose and image quality.

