To demonstrate the feasibility to monitor metastatic bone disease in castration resistant prostate cancer more accurately than regular single energy CT, single phase dual energy CT and technetium bone scans a quantitative analysis of iodine uptake will be performed. ROC statistics will be calculated to find optimal threshold of this biomarker. Qualitative analysis will be done by multiple readers in blinded fashion to determine sensitivity and specificity for distinction between disease progression at first follow-up three month after initiation of therapy. Findings will be correlated with technetium based bone scans.

To analyze the feasibility to detect bone metastasis at baseline more accurately, unenhanced bone marrow imaging will be calculated and additional dual energy based, calcium corrected iodine maps will be used to determine a threshold for detection of vital bone metastasis in order to calculate color coded bone maps for risk of presence of bone metastases. Qualitative analysis will be done by multiple readers in blinded fashion to determine sensitivity and specificity.

To analyze iodine uptake of soft tissue metastasis more accurately and monitor its change during therapy, a ROI based analysis will be performed for suspect metastatic lesions at three time points to see effects of therapy and to distinguish between partial remission, stable disease and progressive disease. A blinded multi reader assessment of iodine maps will be performed to calculate sensitivity and specificity for qualitative analysis of dual energy based examination compared to single-energy CT.

As an exploratory objective we want to determine whether dual energy CT has prognostic capabilities when assessing bone marrow metastases and soft tissue metastasis in terms of therapy response and overall survival. This exploratory objective will require long term follow up and access to patient data exceeding the time period of the baseline and first two follow up CT examinations. Caplan Mayer curves will be drawn and correlated with findings of bone marrow analysis.

Another exploratory objective is to correlate whether adjusted iodine quantification is a viable biomarker for early detection of lymph node metastases, which are too small to fulfill RECIST criteria of a metastasis at baseline but will become evident on follow up. A ROI analysis will be performed to assess whether adjusted iodine uptake might be a viable biomarker for early detection of lymph node metastases.

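### Do the unstated unit of analysis, reader number and read-combination rule leave the planned sensitivity and specificity in need of a plan change?

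*Combined protocol and SAP*

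**What the plan says.** Section 5 (Data Analysis & Statistical Considerations) plans sensitivity and specificity in three places.

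- Bone progression: "Qualitative analysis will be done by multiple readers in blinded fashion to determine sensitivity and specificity for distinction between disease progression at first follow-up".
- Baseline bone detection: calcium-corrected iodine maps "will be used to determine a threshold for detection of vital bone metastasis in order to calculate color coded bone maps", and blinded readers again supply sensitivity and specificity.
- Soft tissue: "a ROI based analysis will be performed for suspect metastatic lesions at three time points to see effects of therapy" (ROI is region of interest), and the purpose is "to distinguish between partial remission, stable disease and progressive disease". The next sentence adds the reader study: "A blinded multi reader assessment of iodine maps will be performed to calculate sensitivity and specificity for qualitative analysis of dual energy based examination", set against single-energy CT.

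Lymph nodes have a ROI analysis only; no sensitivity or specificity is planned for them. Bone scan findings are to be correlated with the CT findings.

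Design & Procedures says: "Patients will be examined with a dual-energy protocol at baseline (i.e., before starting therapy), and during the first and second follow up scans", and gives the purpose as "in order to differentiate between patients with partial remission, stable, or progressive disease". Section 6 (Data & Safety Monitoring) says only that radiologists at the institution score the images.

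The named methods are ROC analysis for a threshold, a multi-parametric regression, correlation with bone scan, and survival curves. Section 5 assigns the statistical analysis to a collaboration with the biostatistics department. The only count in the document is the 150 eligible patients to be contacted. The title page calls the study a pilot of feasibility.

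**The concern.** Sensitivity and specificity are the stated outputs of the reader analyses, and the same set of reads can give different values. The value depends on whether the unit is a lesion or a patient, how many readers there are, and whether reads are averaged, put to a majority or combined in some other way. If that choice is made after the reads are seen, an outsider cannot tell a neutral choice from a favourable one.

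The clearest gap is in soft tissue. Measurements are made on lesions, while Design & Procedures treats partial remission, stable disease and progression as classes of patients. No rule leads from several lesions to one class.

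Separately, if lesions or reads were entered as independent rows, single-modality intervals would be too narrow. Contrasts between modalities that ignored pairing would also have the wrong width.

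**Working it through.** There is no planned figure to reproduce: the documents give no sample-size derivation, expected accuracy, reader count, lesion count or correlation. The check has two parts.

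**1. What the text already settles**

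| Analysis | What the text points to | What stays open |
|---|---|---|
| Bone progression | Patient: Background & Significance defines progression by the PCWG3 2+2 rule | Reader number, how reads are reported, pairing |
| Baseline bone detection | Location or lesion: a threshold feeding colour-coded maps | Unit not named; reader handling |
| Soft tissue | ROI on lesions; response classes belong to patients | Step from lesions to patient; unit of reader accuracy; reader handling; pairing |
| Lymph nodes | A node followed until it becomes evident | Unit of the ROI analysis only; no sensitivity or specificity planned |

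**2. How much the open choices could matter (all inputs assumed)**

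*Combining reads.* Per-read sensitivity is 0.80 and specificity 0.90, with three readers and between-reader correlation ρ = 0.6. Calls are beta-binomial with a = p(1−ρ)/ρ and b = (1−p)(1−ρ)/ρ, where p is the probability of a positive call.

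- Diseased, p = 0.80: a = 0.533, b = 0.133. P(no reader positive) = 0.20 × 0.68 × 0.80 = 0.109, so any-reader sensitivity is 0.891. P(all positive) = 0.80 × 0.92 × 0.95 = 0.699. Majority gives 0.810.
- Non-diseased, p = 0.10: P(no reader positive) = 0.90 × 0.96 × 0.975 = 0.842, which is any-reader specificity. Unanimous gives 0.950 and majority 0.907.
- Mean of readers: 0.80 and 0.90, whatever the correlation.

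Mean and majority therefore differ by about 0.01. The spread of 0.891 − 0.699 = 0.19 in sensitivity comes from the any-reader and unanimous rules. The plan names neither, and never says that reads will be combined. Reporting each reader's result needs no combination rule.

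*Lesion to patient.* Per-lesion specificity is 0.90, with five candidate lesions, intraclass correlation (ICC) 0.3 and an any-lesion rule: 0.900 × 0.930 × 0.946 × 0.956 × 0.963 = 0.729 per patient. The range is 0.48 to 0.83 over 3 to 10 lesions and ICC 0.1 to 0.5. For baseline bone detection this would require metastasis-free patients with several candidate lesions each. The title and objectives describe patients who have osseous metastases, although the inclusion criteria do not require them. Few patients may therefore be available for a per-patient specificity at all.

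*Pooling lesions as independent rows.* True SE / naive SE = √(1 + (m−1)·ICC). With m = 5 and ICC 0.3 this is √2.2 = 1.48, and a nominal 95% interval covers 2Φ(1.96/1.48) − 1 = 81%. The ratio runs from 1.10 (m = 3, ICC 0.1) to 2.35 (m = 10, ICC 0.5). The plan does not say that rows will be pooled and names no interval.

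*Ignoring pairing of modalities.* True SE / naive SE = √((1−r) + (m−1)(ρ₁−ρ₂)). Here r is the correlation for the same lesion across modalities, ρ₁ for different lesions in one modality, and ρ₂ for different lesions across modalities. With m = 5, ρ₁ = 0.3 and r = 0.5:

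- ρ₂ = 0.3 gives √0.5 = 0.71.
- ρ₂ = 0 gives √1.7 = 1.30.

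The ratio lies on either side of 1, so even the direction of error is unknown. With one row per patient it is √(1−r), or 0.84 to 0.55 for r from 0.3 to 0.7, so an unpaired analysis would be conservative.

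Every interval result above requires an analyst to do something the plan does not ask for.

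**The case for a change.** The strongest case for a change has three parts. Pilot status excuses the lack of a powered test but not undefined outputs. The stated aim is to monitor bone disease more accurately than single-energy CT, single-phase dual-energy CT and bone scan. Patients also accept an extra unenhanced scan at each of three visits, about 30 mSv in all. On this view the accuracy values should be defined before anyone reads a scan, and a few sentences would do it.

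Part of this stands. The unit, the reader number and the step from soft-tissue lesions to a patient class are unwritten, and nothing was redacted that would explain it. A choice made after the reads carries less weight than one made before.

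The rest does not show a fault in the plan. The radiation exposure is the same however accuracy is tabulated. A sensitivity reported per reader, with its unit named, is a definite quantity that the audience can interpret. Cluster bootstrap, GEE, mixed models and multi-reader multi-case analysis are all acceptable routes, and writing one in would replace no stated method. Nor is the gain uniform. In simulation with an assumed 30 patients, 3 lesions each and ICC 0.1, the cluster bootstrap covered 0.925 against 0.926 for the naive interval. With 5 lesions and ICC 0.3 it covered 0.940 against 0.803. The gain is real only where lesions are many and correlated, and a statistician who sees several lesions per patient would allow for that without being told.

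**Conclusion.** No change follows. The omissions are genuine, but they are details that analysts can fill soundly within the plan as written: results by reader, with lesion or patient named, and any interval or modality contrast clustered on and paired within patient. No stated rule gives a wrong number, and no sample size, test or decision in the documents rests on the missing details.

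Between the two ordinary summaries, mean and majority, the choice moves sensitivity and specificity by about 0.01 in the central illustration. Larger shifts require any-reader, unanimous or any-lesion rules, or pooled rows, none of which the plan proposes. All these sizes rest on assumed accuracy, reader and lesion counts, and correlations.

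The conclusion assumes that the collaborating statisticians handle within-patient correlation in the usual way. A report that pooled lesions as independent, or presented an any-reader result as the main accuracy figure without saying so, would be open to criticism on that ground.
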